Early administration of basal insulin has seldom been studied in DKA management. In 2012, Hsia et al (4) conducted a prospective randomized controlled trial involving 61 hospitalized adults with known diabetes and presented by hyperglycemia who were randomized to receive treatment with IV insulin infusion (IVII) with or without glargine (0.25 Unit/kg). The primary outcome of rebound hyperglycemia was reduced with early administration of glargine (33.3% vs 93.5%, $P < 0.001$) without increasing the risk of hypoglycemia (none in the intervention group vs three cases in the control group). Accordingly, in 2013, the Joint British Diabetes Societies updated their guideline on DKA management in adults to advise early administration of home basal insulin dose (5). After that, two randomized controlled trials were published in 2015, both with a sample size of 40 patients, investigated initiating Insulin Glargine within 2-3 hrs from IVII initiation compared to IVII alone, using a dose of 0.3 unit/kg (6) and 0.4 unit/kg (7). Although both the studies did not demonstrate statistical significance in the primary and secondary outcomes, it could be argued they were clinically significant. For examples, time to AG closure 13 +/- 6 vs 16 +/- 6 hours, IVII dosage 84 ±45 U vs 116 ± 91 U, rebound hyperglycemia for 24 hours after DKA resolution 35% vs 51%, hospital LOS 5.1 vs 5.9 days (intervention and control groups respectively) (7) and no difference in hypoglycemia events between both groups in both studies.

The limitations in the previous studies such as being underpowered, flaws in reporting data, and lacking a unified management protocol make it difficult to state a definitive evidence-based recommendation for using basal insulin early in DKA in adults. For that reason, we propose prospective, open-label, intervention cohort study to test our hypothesis that an insulin glargine dose of 0.4 Units/kg early administered (within four hours) of IVII initiation in DKA management in adult would be effective and safe in shortening the time to anion gap closure comparing to the standard practice.

II. STUDY OBJECTIVE(S): INCLUDING SPECIFIC AIMS AND/OR HYPOTHESES

Specific Aim 1: Test the hypothesis that early Glargine 0.4 unit/kg administration within 4 hours from IV insulin initiation will provide faster anion gap closure in Diabetic Ketoacidosis management in MICU, at least 20% than late administration.

Specific Aim 2: Determine the safety of insulin glargine 0.4 unit/kg early administration within four hours from IV Insulin infusion initiation.

III. METHODS

A. Study Design and Methodology:

This will be a prospective, open-label, intervention cohort study including all consecutive adult patients with Diabetes Ketoacidosis (DKA) getting admitted to Fairview Hospital-Medical Intensive Care Unit (FV-MICU). Screening of patient eligibility and informed consent will be done by the MICU admitting physician once the patient gets admitted to MICU. Participants will be given an overview of the study, including study procedures, and potential risks. Participants will be given adequate time to review the consent form and have opportunities to ask questions. After the informed consent process has been completed and a consent form has been signed, a copy of the consent will be provided to the participant and another copy will be secured in the Principle Investigator office in a locked cabinet. Enrolled participants in the intervention group will receive an Insulin Glargine 0.4 Unit/kg within 4 hours from initiating the IV Insulin Infusion, as per the Cleveland Clinic DKA protocol. The remaining of the management will be following the CC DKA protocol including continuing IVII till Anion Gap Closure ($AG \leq 12$), Basal Metabolic Panel Q 2 hrs, and replacing electrolytes as indicated. After closing the anion gap, the decision for giving more Basal Insulin doses will be left to the treating physician's discretion. For patient safety, Point Of Care (POC) blood glucose will be checked hourly before IVII discontinuation. After IVII discontinuation, the BG will be checked with meals, bedtime and 2 am if the patient maintain good oral intake, if not, the BG will be checked q 4 hrs. Target BG 150 – 200 mg/dl during the DKA management and 140 – 180 mg/dl after DKA resolution as per American Diabetes Association recommendations. In case of any hypoglycemia event, this goal will be achieved by using Dextrose containing fluid or carbohydrate enriched oral intake which will be left to the treating physician discretion depending on patient awareness and severity of hypoglycemia. Also, the pre meals and correctional insulin doses after AG closure will be left to the treating physician's discretion. After AG closure the pre meals and correctional insulin doses will be left to the treating physician's discretion. In case of not closing the AG after 24 hours from the initial Glargine dose, the decision for further Glargine doses will be left to the treating physician's discretion.

The investigator team will be notified by the MICU attending after each participant enrollment, so one of the team members will present to MICU to collect the data prospectively in a standardized Data Collecting Sheet (DCS) by using REDCap and all protected health information (PHI) will be de-identified. As regards the control group, an E-research request will be submitted to provide a list by

all the consecutive adult patients admitted to FV-MICU with a diagnosis of DKA in the period between January 1st 2019 till the date of IRB approval. Prespecified sample size and matched in basal patient characteristics and DKA severity will be selected as the control group. Data will be collected retrospectively for the control group and will be recorded directly into the DCS in RedCap. Clinical outcomes will be compared between the intervention and control groups. The primary outcome includes time to anion gap closure ($AG \leq 12$). Secondary outcomes include hospital Length Of Stay (LOS), ICU LOS, total IVII dose, the incidence of transitional failure (defined recurrence of DKA after initial IVII discontinuation within 24 hours and requiring reinitiating the IVII), the incidence of hyperglycemia (> 180 mg/dL) and hypoglycemia (defined as ≤ 70 mg/dL, <54 , <40) during 24 hours from Insulin Glargine administration.

B. Definition of main exposures and outcomes:

Diagnosis of DKA will be made by ICD-10-CM code E10.10, E11.10, or meeting the ADA definition; $BG \geq 250$ mg/dl, $AG > 12$, and positive Ketones in serum or urine

DKA classification as the following table from ADA:

	Mild (plasma glucose >250 mg/dl)	Moderate (plasma glucose >250 mg/dl)	Severe (plasma glucose >250 mg/dl)
Arterial pH	7.25–7.30	7.00 to <7.24	<7.00
Serum bicarbonate (mEq/l)	15–18	10 to <15	<10

For the hyperglycemia analysis, patients will be compared in the following categories according to their mean or median (depending on the normality of the data distribution) blood glucose throughout the hospital stay:

- Mean/median BG <80 mg/dL
- Mean/median BG 81-100 mg/dL
- Mean/median BG 101-140 mg/dL
- Mean/median BG 141-180 mg/dL
- Mean/median BG > 180 mg/dL'
- Mean/median BG > 240 mg/dL

Hypoglycemia will be defined by three categories:

- any glucose level below 70 mg/dL
- any glucose level less than 54 mg/dL
- any glucose level less than 40 mg/dL

For Time of Anion Gap Closure (TAGC) will use the ADA definition: $AG \leq 12$ mEq/L

Transitional failure will be defined as the recurrence of DKA ($BG \geq 250$ mg/dl, $AG > 12$, and positive Ketones in serum or urine) after initial IVII discontinuation within 24 hours and requiring reinitiating the IVII.

C. Study Population

Intervention vs Control group

- Intervention group: All consecutive adult patients getting admitted to FV- MICU and meet the inclusion criteria and accepted to receive insulin glargine early as per the protocol. They will receive insulin glargine 0.4 unit/kg within 4 hours from initiating the IV Insulin Infusion, as per the Cleveland Clinic DKA protocol.
- Control group: prespecified and matched sample size, consecutive adults who admitted to FV-MICU with a diagnosis of DKA in the period between January 1st 2019 till the IRB approval date and didn't receive basal insulin before AG closure.

Inclusion criteria:

- Age \geq 18 years old
- Meet DKA definition as above
- Having the capacity to sign Informed consent

Exclusion Criteria

- IV insulin infusion initiated more than 4 hours.
- Persistent hypotension (SBP<80 mmHg despite receiving 1000cc normal saline).
- Require Vasopressor
- Acute Coronary Syndrome
- Pregnant
- End-stage renal disease
- Unwilling to consent to participate in the trial
- Currently under police custody
- Transferred from another hospital
- Require emergent surgery
- Alcoholic Ketoacidosis

Study Variables:

General Informations:

- Patient name
- MRN
- Age
- Sex (Male, Female, Others)
- Race (White, Black, Asian, Other)
- Ethnicity (Hispanic vs. Non-Hispanic)
- Weight on admission (kg)
- BMI (Kg/m²)
- Height (cm)
- Date of Hospital admission
- Date of ICU admission

- Date of DKA diagnosis (MM/DD/YY)
- Precipitating cause of DKA
 - Noncompliance
 - New-onset
 - Infection
 - Cerebrovascular accident
 - alcohol abuse
 - pancreatitis
 - Drugs
 - Others

Past Medical history

- Type of diabetes:
 - Type 1 DM
 - Type 2 DM
 - Cystic fibrosis-related diabetes
 - Steroid-induced diabetes
 - Other or no clear diagnosis
- Known diagnosis of other major medical comorbidities (CAD, CHF, HTN, COPD, asthma, liver disease, CKD, cancer, other)
- On Renal Replacement Therapy (Y/N)
- Using Basal insulin at home (Yes/No/ unknown)
- If previous point answer is yes check the corresponding insulin type and write the dose: (Glargine, Detemir, Degludec, NPH, Continuous Insulin Pump) (dose: IU)
- Home total basal insulin dose (units)
- Non-insulin antihyperglycemics taken at home prior to admission, including the type
 - Sulfonylureas
 - Thiazolidinediones
 - Dipeptidyl peptidase-4 (DPP-4) inhibitors
 - Biguanides
 - Glucagon like peptide-1 (GLP-1) analogues
 - Sodium-glucose transport protein 2 (SGLT2) inhibitors
 - Meglitinides
 - Alpha glucosidase inhibitors
 - Amylin analogues
- History of immunosuppression (history of cancer, HIV or auto-immune disease or organ transplant, chronic steroid)

Initial Laboratory values:

- Anion gap (mEq/L)
- Bicarbonate (mEq/L)
- Glucose (mg/dL)
- Beta-Hydroxybutyrate (mmol/L)
- Ketones in the urine (Y/N/Unknown)
- HbA1c %
- Lactate (mmol/L)

Intervention and outcomes:

- IV insulin infusion starting time
- Insulin glargine administration time
- Anion Gap closure time
- IV insulin discontinuation time
- Number of hours of IVII
- Total IV insulin infusion has been given
- Total IV insulin/weight
- Total IV fluid during DKA management
- Date of discharge from ICU
- Date of discharge from hospital
- Hospital Length Of Stay (days)
- ICU LOS (hours)
- Transitional failure (recurrence of DKA)?

Hypoglycemia Events

- Hypoglycemia event within 24 hrs from glargine
- Time of the hypoglycemia
- How many hours after the glargine administration?
- Severity
- How it has been treated

Hyperglycemia Events

- Hyperglycemia Event after IVII discontinuation by 24 hours (Y/N)
- time of the hyperglycemia event
- Severity of hyperglycemia
- How many hours after IVII discontinuation

D. Outcomes

Primary outcome: Time to anion gap closure (hours).

Secondary outcomes:

- Hospital Length of stay (days)
- ICU length of stay (hours)
- Total IV insulin infusion dose (International unit)
- Incidence of transitional failure (percentage).
- Incidence of hyperglycemia (> 180 mg/dL) during 24 hours from Insulin Glargine administration (percentage).
- Incidence of hypoglycemia (defined as ≤ 70 mg/dL, <54, <40) during 24 hours from Insulin Glargine administration (percentage).

IV. DATA COLLECTION

For the control group, the data will be collected retrospectively and recorded in standardized DCS in RedCap. For the intervention group, the data will be collected prospectively by the investigator team members and observations will be recorded in standardized DCS in RedCap. All protected health information (PHI) will be de-identified for both intervention and control group by using de-identification function in REDCap.

V. DATA ANALYSIS

The sample size calculation considered the average time of AG closure in the last 3 months in FV-MICU was 15.6 ± 2.5 hours (CI 95%) and SD of 6 hours. Using one-sided α of 0.025 and an β of 0.10, an expected 20% difference between the two groups, a sample size of 160 totally of the participant will be adequate.

Categorical variables will be described as frequency rates and percentages, and continuous variables will be described using mean, median, and interquartile range (IQR). Proportions for categorical variables will be compared by Chi-squared test of Fisher's exact test. Means for continuous variables will be compared by Student's t-test if normally distributed and Mann-Whitney test if not normally distributed. All statistical analyses will be performed with a one-sided p-value < 0.025 to determine statistical significance. All statistical analyses will be completed by study investigators using Statistical Analysis Software (SAS).

VI. DATA AND SAFETY MONITORING PLAN (if applicable)

All data will be stored in a secured REDcap database. No PHI will be saved on non-HIPAA protected devices. All protected health information (PHI) will be de-identified by using RedCap.

To ensure patient safety, CCF Hypoglycemia protocol is getting followed in all patients receiving insulin including our enrolled participants. Before IV insulin discontinuation, the blood glucose level is getting checked hourly as per protocol. Once the AG is closed and insulin infusion is discontinued, the patient who is maintaining oral intake, blood glucose will be checked with meals, bedtime, and 2 am. If the patient having poor oral intake, blood glucose will be checked q 4 hours. Different treatment options for any hypoglycemic events are available in the protocol depending on the severity of the hypoglycemia event and patient awareness, ranging from oral carbohydrate supplement to IV fluid containing dextrose.

VII. STUDY LIMITATIONS

- Retrospective EPIC data review for the control group. Single-center.

VIII. ETHICAL CONSIDERATIONS

For patient safety, insulin therapy is carrying a risk of hypoglycemia events. Previous studies didn't show any additional risk when insulin glargine has been given before anion gap closure comparing to the common practice, after anion gap closure. Shankar and Hsia's studies (4, 8) didn't reveal any hypoglycemic events between both groups. Both Doshi and Houshyar's studies (6, 7) revealed similar hypoglycemic events between both intervention and control groups and were neither clinically nor statistically significant.

The possible explanation for that is although the overlap time of glargine and IV insulin infusion is longer in the intervention group, the insulin infusion rate is getting adjusted hourly to meet the body requirement to decrease the blood sugar by a range of 50 - 100 mg/dl per hour. To ensure patient safety, CCF Hypoglycemia protocol is getting followed in all patients receiving insulin including our enrolled participants. Before IV insulin discontinuation, the blood glucose level is getting checked hourly as per protocol. Once the AG is closed and insulin infusion is discontinued, the patient who is maintaining oral intake, blood glucose will be checked with meals, bedtime, and 2 am. If the patient having poor oral intake, blood glucose will be checked q 4 hours. Different treatment options for any hypoglycemic events are available in the protocol depending on the severity of the hypoglycemia event and patient awareness, ranging from oral carbohydrate supplement to IV fluid containing dextrose. After AG closure the pre meals and correctional insulin doses will be left to the treating physician's discretion.

For data safety, all data will remain anonymous, and no personal health information will be associated with any data resulting from this study. Data will recorded directly into a secure REDCap database. No PHI will be saved on non-HIPAA protected devices. All protected health information (PHI) will be de-identified by using RedCap.

All subjects will be provided a consent form describing this study and with sufficient information to make an informed decision about participation in the study. The consent form will be submitted with the protocol for review and approval by the IRB. The formal consent of a subject, using the IRB-

approved consent form, will be obtained before the subject undergoes any study procedure. This consent form must be signed by the subject, and the investigator-designated research staff obtaining the consent.

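### Aim 2 asks about safety, but the listed outcomes and variables cover only glucose events and DKA recurrence; potassium is not among them

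*Combined protocol and SAP*

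**What the plan says.** Section II, Specific Aim 2, is to "Determine the safety of insulin glargine 0.4 unit/kg early administration within four hours from IV Insulin infusion initiation". It names no endpoint, threshold or margin.

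The secondary outcomes (Sections III.A and III.D) are hospital stay, ICU stay, total IVII dose, transitional failure, hyperglycemia and hypoglycemia. Three of these can be read as harms:
- "Incidence of hypoglycemia (defined as ≤ 70 mg/dL, <54, <40) during 24 hours from Insulin Glargine administration (percentage" (III.D)
- "Incidence of hyperglycemia (> 180 mg/dL) during 24 hours from Insulin Glargine administration (percentage" (III.D)
- "Transitional failure will be defined as the recurrence of DKA" (III.B), judged on glucose, anion gap and ketones

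For routine care during the infusion, Section III.A specifies "Basal Metabolic Panel Q 2 hrs, and replacing electrolytes as indicated". After the infusion stops, Sections III.A, VI and VIII schedule glucose checks only.

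In the study variables (III.C), the block headed "Initial Laboratory values" holds anion gap, bicarbonate, glucose, beta-hydroxybutyrate, urine ketones, HbA1c and lactate. The event fields are of one kind: "Hypoglycemia event within 24 hrs from glargine" and its details, with a parallel block for hyperglycemia. The monitoring plan (VI) rests on glucose: "To ensure patient safety, CCF Hypoglycemia protocol is getting followed in all patients receiving insulin including our enrolled participants". The ethics section (VIII) discusses hypoglycemia as the risk of insulin and no other.

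**The concern.** Safety is a broader claim than absence of low glucose. That insulin lowers serum potassium is general pharmacology and is not stated in the protocol, but the protocol does foresee electrolyte replacement. A change in potassium is therefore a foreseeable harm of giving insulin, and the lists give no way to compare it between groups. No electrolyte, arrhythmia or general adverse-event field would pick it up indirectly.

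What is at stake is the conclusion of Aim 2. If hypoglycemia proves similar in the two groups, the report could state that early glargine 0.4 unit/kg is safe, and the data would support only a statement about glucose. Baseline potassium would also be missing from the comparison of treated patients with historical controls. Whether it differs between them, or matters for closure time, is unknown.

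**Working it through.** **1. The plan's own figure.** Section V gives a mean closure time of 15.6 h, SD 6 h, a 20% difference, one-sided α 0.025 and β 0.10.
- Difference: 0.20 × 15.6 = 3.12 h, so the expected intervention mean is 12.48 h.
- n per group = 2 × (1.960 + 1.282)² × 6² / 3.12² = 77.7, rounded up to 78, or 156 in total.
- The t-based version gives 79 per group, 158 in total.
- Power at 80 per group is 0.908.

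The stated 160 is reproduced. This point exposes no arithmetic error.

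**2. Outcomes and variables set against the aim.**

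| Place | Possible harms covered | Potassium |
|---|---|---|
| III.A, III.D outcomes | hypoglycemia, hyperglycemia, transitional failure | none |
| III.C initial laboratory values | not applicable | none |
| III.C event fields | hypoglycemia, hyperglycemia | none |
| VI monitoring, VIII ethics | hypoglycemia | none |
| III.A routine care | electrolytes replaced | implied by the panel |

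The word potassium does not occur in the text. That it is measured follows from its being a standard component of a basic metabolic panel, which is how the protocol's term is read here.

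**3. Data that should already exist.** One panel every 2 h to closure gives 12.48/2 = 6.2 per intervention patient and 15.6/2 = 7.8 per control. Over 80 intervention patients (1:1 is an assumption) that is 80 × 6.24 ≈ 499 values. If glargine is given at the 4 h limit, the values after it number about 80 × (12.48 − 4)/2 ≈ 339.

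**4. Why the window matters.** If glargine works as hoped, treated patients have 6.24/7.8 = 0.80 times as many scheduled panels to closure. A lowest value, or any value below a cut-off, is more likely to be found with more draws. Counting to closure would therefore favour the faster group even with no true difference. A window running past the end of the infusion would rely on unscheduled draws, which may differ between prospectively followed patients and historical charts.

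**5. Precision of a hypokalemia outcome.** The documents give no rate, so a range is assumed, with 80 per group.
- 95% CI half-width for a difference, equal rates p: 1.96 × √(2p(1 − p)/80).
- Power for a 10-point rise from p₁ to p₂, one-sided 0.025: Φ{[0.10√80 − 1.96√(2p̄(1 − p̄))] / √(p₁(1 − p₁) + p₂(1 − p₂))}, where p̄ is the mean of p₁ and p₂.

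| Assumed control rate | CI half-width | Power for +10 points | Rate detectable with 80% power |
|---|---|---|---|
| 10% | 9.3 points | 42% | 27% |
| 20% | 12.4 points | 31% | 40% |
| 30% | 14.2 points | 26% | 52% |

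Even zero events in 80 would leave a one-sided 97.5% upper limit of 1 − 0.025^(1/80) = 4.5%.

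**The case against.** The case against has several parts.

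- **Patients are not unprotected.** Electrolytes are checked and replaced in routine care. This stands. The gap is in what the study records and compares, not in monitoring. Replacement can also mask a difference in potassium, so the amount replaced is needed too.
- **The Data Collecting Sheet is not shown.** Section XI lists it as an appendix, and a potassium field there cannot be ruled out. A reader might infer that potassium is never captured; the documents do not support that. The detailed variable list in the protocol body omits it, and no outcome uses it.
- **Glucose alone is an inference.** Aim 2 is linked to no endpoint, and transitional failure also uses anion gap and ketones. It measures DKA recurrence, though, and cannot detect hypokalemia.
- **Early glargine need not mean more insulin.** A reader might infer a clearly higher total insulin exposure. In the earlier 0.4 unit/kg trial cited in the background, IV insulin was 84 U with glargine against 116 U without. At an assumed 60–90 kg, 0.4 unit/kg is 24–36 U, giving 108–120 U against 116 U before any later basal dose. These figures do not establish a higher load.
- **Titration may take account of potassium.** A reader might infer from Section VIII, which describes hourly adjustment to glucose, that titration ignores potassium. Treatment follows an institutional DKA protocol that is not reproduced, so this is unknown.
- **Precision is poor.** This stands. The outcome would show only large differences.

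**Conclusion.** The point holds in a limited form. As the protocol body stands, Aim 2 promises a safety finding, while the listed data can address only glucose events and DKA recurrence. Potassium, a foreseeable insulin-related concern that routine panels should already measure, is absent from every outcome and variable list. The change is worth making because it is cheap and alters what Aim 2 can conclude; it does not threaten the primary result.

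This rests on reading the panel as including potassium and on the unseen data sheet matching the variable list. The 9–14 point half-widths depend on 1:1 allocation and assumed rates of 10–30%. Any effect of baseline potassium on closure time is plausible but not shown by the documents.

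**What to change.** Add to the study variables and data sheet, for both groups:
1. baseline potassium;
2. lowest potassium in one common fixed window that starts at IVII start and is confined to the period when 2-hourly panels are scheduled;
3. the number of potassium values in that window;
4. total potassium replaced.

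The window starts at IVII start because controls have no early glargine dose. Fix its length before data review, short enough that most patients in both groups are still under 2-hourly panels. Compare the groups over that same span, so that earlier closure with fewer draws does not make one group look safer.

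Report hypokalemia as a secondary safety outcome under Aim 2, at cut-offs fixed before any data are reviewed, including the control charts. Present the difference with its 95% CI and do not offer a non-significant result as proof of safety. If the data sheet already holds potassium, bring the protocol's lists into line with it.

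If these fields are not wanted, narrow Aim 2 to hypoglycemia after early glargine.

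The cost is a few more chart-abstraction fields, one more table, and intervals that will be wide. Sample size, treatment and sampling do not change.

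### Anion gap closure can be timed only at panel draws, and the plan neither shows that historical controls were drawn as often as enrolled patients nor lists the draw times needed to check

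*Combined protocol and SAP*

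**What the plan says.** Section III.A states the outcome: "The primary outcome includes time to anion gap closure". Section III.B adds only the threshold: "For Time of Anion Gap Closure (TAGC) will use the ADA definition", that is, AG of 12 mEq/L or less. Neither section says which draw marks closure or how time between draws is handled.

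For enrolled patients, section III.A says: "The remaining of the management will be following the CC DKA protocol including continuing IVII till Anion Gap Closure". The same sentence goes on to "Basal Metabolic Panel Q 2 hrs, and replacing electrolytes as indicated". The 2-hourly panel is therefore presented as part of the hospital (CC) DKA protocol, which the study adopts.

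Controls are DKA admissions to the same MICU from January 2019 to IRB approval. Section III.A says "Data will be collected retrospectively for the control group". Section III.C requires that they "didn't receive basal insulin before AG closure", but gives no panel interval and does not say that they were managed under the CC DKA protocol.

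Under the outcome variables in section III.C, the relevant entry is "Anion Gap closure time". The list has no draw times, no number of draws and no last panel with the gap still open. Section V plans a t-test or Mann-Whitney test. Section VII names retrospective chart review of controls as a limitation, but does not mention laboratory timing.

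**The concern.** True closure lies somewhere between the last panel with AG above 12 and the first at or below 12. A single charted closure time is most naturally the upper end of that interval, so it is late, and the lateness grows with draw spacing. If both groups are drawn equally often, the lateness cancels. If controls were drawn less often, their closure looks later with no difference in physiology, and the comparison tilts toward early glargine.

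Matching on baseline characteristics and DKA severity does not help, because the distortion arises when the outcome is measured. The planned tests treat the recorded times as exact. With no draw times among the listed variables, the analysis as written would neither reveal nor correct a difference in spacing.

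**Working it through.** **Inputs from section V.** Mean closure time 15.6 h, SD 6 h, expected difference 20%, one-sided alpha 0.025, power 0.90, total 160.

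**Assumptions.** Allocation is not stated, so 1:1 (80 per group) is assumed. The control draw interval is not given, so 2 to 6 h is assumed. Draws fall at random relative to true closure, and every enrolled patient is drawn 2-hourly. The 15.6 h and 6 h are treated as the mean and SD of true closure times.

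**The plan's own figure.** Target difference = 0.20 × 15.6 = 3.12 h. Per group, n = 2 × (1.960 + 1.282)² × 6² / 3.12² = 77.7, so 78 per group and 156 in total. The t-test version gives 79 per group, 158 in total. The stated 160 is reproduced, and power at 80 per group is about 91%. Draw timing does not make the sample size wrong.

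**Artefact.** For draw interval c, the recorded time exceeds the true time by c/2 on average. With 2 h in enrolled patients and c in controls, the spurious difference is (c − 2)/2.

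**Effect on the test.** Random draw timing adds variance c²/12. The standard error is therefore √[(36 + 2²/12)/80 + (36 + c²/12)/80], close to the simple 6 × √(2/80) = 0.949 h. One-sided error = Φ(artefact/SE − 1.96).

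| Control interval (assumed) | Artefact | Share of 3.12 h | SE | One-sided error, formula | One-sided error, simulation |
|---|---|---|---|---|---|
| 2 h | 0 h | 0% | 0.953 h | 2.5% | 2.4% |
| 3 h | 0.5 h | 16% | 0.956 h | 7.5% | 7.3% |
| 4 h | 1.0 h | 32% | 0.960 h | 18% | 18.0% |
| 6 h | 2.0 h | 64% | 0.970 h | 54% | 53.9% |

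The simulation used 20,000 trials per row, gamma closure times with mean 15.6 h and SD 6 h, 80 per group and no true effect.

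**Partial slippage.** If half the controls were drawn every 2 h and half every 4 h, the simulated artefact is 0.49 h and the error 7.4%.

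**Slippage in enrolled patients.** In general the artefact is (control interval − enrolled interval)/2. With enrolled patients at 3 h and controls at 4 h, it is (4 − 3)/2 = 0.5 h rather than 1.0 h.

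**Midpoint timing.** Replacing the first-observed time by the interval midpoint kept the simulated error between 2.4% and 2.7% for all these control intervals.

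**The case against.** The strongest reply is that the 2-hourly panel is not a research schedule. Section III.A takes it from the hospital's DKA protocol, and the controls come from the same MICU. Sections VI and VIII also describe glucose monitoring as institutional routine. Routine care of controls may itself have been 2-hourly, in which case there is no bias. This stands. A reader might infer that only the intervention group had 2-hourly draws, or that the primary outcome is already biased; the documents support neither. They also do not show that the protocol was in force, or followed, throughout the control period.

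Four further points stand in part:

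- That closure means the first qualifying panel is an inference. It is the natural reading of one charted time, but the plan does not say so.
- A reader might infer that the information is lost. It is not: specimen times should be recoverable from the electronic record. What is missing is a plan to collect them. The Data Collecting Sheet is an appendix whose contents are not in the text available, so the statement here is limited to the variables listed in section III.C.
- The 54% figure is an extreme scenario with fully regular 2-hourly draws in one group and 6-hourly in the other. It should not be read as the trial's expected error rate. Study staff attend to collect data, and the plan does not say that they enforce draw times.
- Midpoint timing corrects fully only when draw timing is unrelated to closure. Draws prompted by clinical state could leave some bias.

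**Conclusion.** The point holds as a conditional risk to the primary comparison. Closure is observable only at draws, a draw interval is written down only for enrolled patients, and nothing listed would show whether controls had the same one. The artefact is zero if spacing was equal. It is 0.5 to 2.0 h, or 16% to 64% of the planned effect, if controls averaged 3 to 6 h against 2 h, with one-sided error of about 7% to 54% in place of 2.5%. These sizes rest on assumed control intervals, 1:1 allocation, SD 6 h and full 2-hourly adherence in enrolled patients; slippage among the latter shrinks them. The direction favours glargine only if controls were in fact drawn less often.

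This is a cheap improvement rather than an established flaw. Confidence is moderate.

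**What to change.** In both groups, replace the single closure time with two specimen-collection times from the electronic record: the last panel with AG above 12 and the first at or below 12. Report the draw interval around closure by group. State whether the CC DKA protocol, with 2-hourly panels, applied throughout the control period.

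In sections III.B and V, define closure time explicitly. Analyse it by an interval-censored or midpoint method alongside the first-observed time, and prespecify which is primary.

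The cost is one extra timestamp per patient, from laboratory results that must be opened anyway to find closure, plus a few sentences and slightly more analysis. It needs no extra blood draws or patients and no change to care. If spacing proves equal, the report will show that this source of bias is absent.
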